9.2.2 Serious adverse events (SAEs)

A serious adverse event is any untoward medical occurrence or effect that:

- results in death;
- is life threatening (at the time of the event);
- requires hospitalisation or prolongation of existing inpatients' hospitalisation;
- results in persistent or significant disability or incapacity, other than the existing disability of the patient;
- is a congenital anomaly or birth defect;
- Any other important medical event that may not result in death, be life threatening, or require hospitalization, may be considered a serious adverse experience when, based upon appropriate medical judgement, the event may jeopardize the subject or may require an intervention to prevent one of the outcomes listed above.

All SAEs will be reported through the web portal *ToetsingOnline* to the accredited METC that approved the protocol, within 15 days after the sponsor has first knowledge of the serious adverse reactions. SAEs will also be reported to the Clinical Representative of the funding agency (NIDCD).

SAEs that result in death or are life threatening should be reported expedited. The expedited reporting will occur not later than 7 days after the responsible investigator has first knowledge of the adverse reaction. This is for a preliminary report with another 8 days for completion of the report.

Notably, (scheduled) hospitalization for reasons of standard care and maintenance of invasive ventilation or other medical technology the participants may use will not be considered an SAE.

9.2.3 Serious Adverse Device Effects (SADEs)

Adverse device effects are all untoward and unintended responses to an investigational device.

Unexpected adverse device effects are SADEs if the following three conditions are met:

1. the event must be serious (see chapter 9.2.2);
2. there must be a certain degree of probability that the event is a harmful and an undesirable reaction to the medicinal device under investigation;
3. the adverse reaction must be unexpected, that is to say, the nature and severity of the adverse reaction are not in agreement with the device information as recorded in the IMDD.

The sponsor will report expedited the following SADEs through the web portal

ToetsingOnline to the METC:

- SADEs that have arisen in the clinical trial that was assessed by the METC;
- SADEs that have arisen in other clinical trials with the same medical device, and that could have consequences for the safety of the subjects involved in the clinical trial that was assessed by the METC.

The remaining SADEs are recorded in an overview list (line-listing) that will be submitted once every half year to the METC. This line-listing provides an overview of all SADEs from the medical device, accompanied by a brief report highlighting the main points of concern. The expedited reporting of SADEs through the web portal *ToetsingOnline* is sufficient as notification to the competent authority.

The sponsor will report expedited all SADEs to the competent authorities in other Member States, according to the requirements of the Member States.

The expedited reporting will occur not later than 15 days after the sponsor has first knowledge of the adverse reactions. For fatal or life threatening cases the term will be maximal 7 days for a preliminary report with another 8 days for completion of the report.

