SUSAR	Suspected Unexpected Serious Adverse Reaction
Wbp	Personal Data Protection Act (in Dutch: Wet Bescherming Persoonsgevens)
WMO	Medical Research Involving Human Subjects Act (in Dutch: Wet Medisch-wetenschappelijk Onderzoek met Mensen

SUMMARY

Rationale

In this pilot study we will provide locked-in people with a new means of communication which has not been possible up to now. For the first time, we will test whether we can record and decode neural signals obtained directly from the brain, for control over a computer. The target population is severely paralyzed, due to trauma, brainstem stroke, neuromotor disease or another cause, and has no means of communication other than for instance eye blinks. This condition is called the locked-in syndrome. For these patients there is no technique available to allow them to communicate unaided. We have developed a brain-computer interface (BCI) system that can read activity directly from the brain, and can convert the activity to a digital switch. The system, called the Utrecht Neural Prosthesis (UNP), consists of an implantable amplifier for electrical brain signals, a set of electrodes positioned on the surface of the brain and a wireless receiver (constituting the 'Medtronic System'). This was recently developed by Medtronic, a company specialized in medical implantable devices such as Deep Brain Stimulators and pacemakers among others, and has been tested for the current application by our group at the UMC. A dedicated computer will convert the signals to electrical pulses for standard Assistive Technology (AT) devices (UMC Brain Interpreter, developed at the UMC with the Medical Technology Dept). The amplifier and electrodes are fully implanted and signal is transmitted wirelessly through the skin. Crucial elements of the UNP are exact positioning of electrodes on the cortex (after accurate localization of two brain functions and associated regions), and the specific features extracted from the complex brain signals. The UNP can in principle enable the patient to engage in any activity that is offered by commercial Assistive Technology companies that can be performed with switch signals, for instance operating home apparatus such as lights, tv, curtains etcetera, or writing text for emailing. Since we do not yet know how proficient participants can operate the BCI system, the ability to switch home devices on or off may not be safe. Therefore for the current pilot study we will initially limit use of the BCI system to making selections on a computer screen, and to writing text. In the course of the study (once patients have reached a certain level of proficiency), the possibility of environmental control (e.g. tv, lights) may be made available to the patient. Decisions about this will be made on an individual basis. Most importantly, we aim to achieve unsupervised function of the BCI, meaning that the patient will be able to use it at home without the aid of researchers or other experts (but with minimal caregiver assistance). The device, consisting of amplifier, electrodes and the wires connecting them to each other, will be implanted in 5 patients. Research will be conducted for 12 months after implant and may be extended if the participant chooses to continue participation.

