8.7 Premature termination of the study

If all of the first three participants fail to reach the first level of BCI performance, being supervised use ([Section 8.1.1](#)), within 6 months after implantation ([Section 2](#)), and convincing solutions for future participants cannot be conceived, we will consider terminating the study prematurely (in consultation with DSMB). In addition, if a serious adverse device effect is reported for two subjects, we will consider terminating the study prematurely (in consultation with the DSMB).

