9.5 Data Safety Monitoring Board (DSMB)

A Data Safety Monitoring Board will be established for this study. It will perform online safety surveillance and performs interim analyses on the safety data. It will consist of a committee

whose members are independent from the research group. The DSMB will consist of experts in the areas of this research, including neurology, implantable devices and ethics.

The task of the DSMB will be to monitor the progress in the study in terms of achieving the stated objectives and improvement of the listed parameters for BCI signal processing. The DSMB meets before the study starts or early in the course of the study, to discuss the protocol, the study, any analysis plan, future meetings, and to have the opportunity to clarify any aspects with the principal investigators. After that, the DSMB will meet at least once a year. Additional meetings may be planned depending on timing of inclusion of patients and progress. One of the (regular or additional) meetings will be scheduled shortly after the first patient has been followed for six months after implantation. The DSMB will be asked to give advice at the decision moment after the third implantation, as to how to proceed based on the obtained results. It is the responsibility of the DSMB to verify adherence of the research team with the procedures as described in the research protocol.

The recommendations of the DSMB are circulated and approved by all DSMB members, then forwarded to the PI and, if deemed necessary, to the Ethics Committee of the UMC.

Criteria for decision to terminate the study prematurely

The key criterion for premature termination of the study (also stated in Sections 4.4, 8.7 and 10.4) is level of proficiency at 6 months after implant ('futility'). In addition the usual criteria are relevant, being unexpected problems with function of the device, unexpected systematic side effects that cause concern ('safety'). In addition the DSMB may decide to advise termination of the pilot study if results are above expectations (i.e. high levels of proficiency in all three first participants, 'positive efficacy'), to expedite a larger clinical trial.

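### Does the two-subject safety review in section 8.7 need to say whether foreseen serious device effects count?

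*Combined protocol and SAP*

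**What the plan says.** Section 8.7 of the combined protocol and SAP holds the only safety criterion with a count: "if a serious adverse device effect is reported for two subjects, we will consider terminating the study prematurely", in consultation with the DSMB. The term is written out in lower case, with no pointer to another section.

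Section 9.2.3 holds the only definition, in two steps. The wider class comes first: "Adverse device effects are all untoward and unintended responses to an investigational device". The narrower class follows: "Unexpected adverse device effects are SADEs if the following three conditions are met". Those conditions are seriousness as in 9.2.2, a degree of probability that the event is a reaction to the device, and that "the adverse reaction must be unexpected, that is to say, the nature and severity of the adverse reaction are not in agreement" with the IMDD.

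Section 9.5 lists the grounds on which the DSMB may advise termination. Besides futility and positive efficacy, it names unexpected problems with device function and "unexpected systematic side effects that cause concern ('safety". It gives no count of subjects and does not use the term SADE.

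**The concern.** The words in 8.7 can be taken in two ways. On the narrow reading they mean the class defined in 9.2.3. A serious device effect that matches the IMDD in nature and severity then never counts towards the two, however many participants have it. On the wide reading they mean any adverse device effect, in the sense of the opening sentence of 9.2.3, that is also serious. Two foreseen effects would then be enough.

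The study has five participants, and section 11.4.1 describes the device as the first implanted for BCI. If the sponsor, the investigators and the DSMB counted different events, the one numerical safety rule would lose its purpose. The name SADE does not contain the word unexpected, so 8.7 read alone gives no hint that foreseen effects might be left out.

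**Working it through.** **Comparing the sections**

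1. Definition. 9.2.3 carries the term in its heading and is the only place that defines it. Reading 8.7 with that definition is the ordinary course, and lower case is weak evidence of a different meaning.
2. Consistency. 9.5, under its own paragraph on premature termination, words the safety grounds around unexpected problems and side effects. That agrees with the narrow reading. No section says that foreseen effects count towards the two, so nothing is contradicted.
3. Force. 8.7 obliges the team only to consider termination, after consulting the DSMB. Nothing stops automatically on either reading, and nothing prevents the same discussion after foreseen events.
4. Cover for foreseen events:
   - Every SAE, expected or not, goes to the METC within 15 days. Fatal or life-threatening ones get a preliminary report within 7 days (9.2.2).
   - The study is suspended pending METC review if the disadvantages may be significantly greater than foreseen (9.1).
   - For the DSMB, "It will perform online safety surveillance and performs interim analyses on the safety data" (9.5).
   - SAEs also enter the annual progress report (12.4).

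**Size of what turns on the reading**

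The plan states no operating characteristic for the two-subject rule, so there is no figure to reproduce. The inputs for an illustration are:

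- n = 5 participants (4.1) and a threshold of 2 (8.7);
- intracranial infection of about 5% and haemorrhage of 0 to 2% (11.4.3). The highest combined risk is 5% + 2% = 7%, if the two never occur together.

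With independent participants and a common risk p, P(at least 2 of 5) = 1 − (1 − p)^5 − 5p(1 − p)^4.

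| p | Calculation | Result |
|---|---|---|
| 0.05 | 1 − 0.77378 − 0.20363 | 0.02259 (2.3%) |
| 0.07 | 1 − 0.69569 − 0.26182 | 0.04249 (4.2%) |
| 0.025 | 1 − 0.88110 − 0.11296 | 0.00594 (0.6%) |
| 0.035 | 1 − 0.83683 − 0.15176 | 0.01141 (1.1%) |

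Assume that all these events are serious and device-related. The wide reading then gives 2.3% to 4.2%. The narrow reading depends on the share that matches the IMDD:

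- all match: 0, so the gap is 2.3 to 4.2 percentage points;
- half match: 0.6% to 1.1%, so the gap is 2.3 − 0.6 = 1.7 to 4.2 − 1.1 = 3.1 points;
- none match: no gap.

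These are upper figures. 11.4.3 presents infection and haemorrhage mainly as risks of the surgery, so they may fail the device-relation condition and count on neither reading. The haemorrhage literature rests mostly on devices that penetrate the cortex. Participants with an existing implant do not have the electrode surgery (3.1, 11.4.1).

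Two of five participants is an observed 40%, eight times a foreseen risk of 5%. A result of that kind is what 9.1 is there to catch, whatever the count in 8.7 includes.

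**The case for a change.** The best case for a change is that a pre-set count is worth having only if everyone counts the same events, and that clarity would cost a few words. 8.7 cites other sections in the sentence before but not here. 9.5 does not mention the two-subject rule, although the DSMB is to be consulted on it; it cites 8.7 only for futility. The naming is awkward too: the heading of 9.2 promises SUSARs, which the abbreviation list expands as "Suspected Unexpected Serious Adverse Reaction", while SADE is missing from that list. Lastly, the half-yearly list rests on the same term ("This line-listing provides an overview of all SADEs from the medical device"), so the narrow reading would keep foreseen serious device effects off it.

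Some of this stands. The cross-reference is missing, and a reader who opens only 8.7 could misjudge its scope. The safeguards for foreseen events rest on judgement, not on a count. The rest carries little weight. Putting the unexpected device class where 9.2 announces SUSARs supports the narrow reading. The METC, which receives the half-yearly list, already gets each SAE individually, so no event is withheld from it. Clearer wording might also leave practice exactly as it is, since the narrow class is the one the text already defines.

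**Conclusion.** This is a gap in cross-referencing that a reader fills sensibly: 8.7 takes the meaning that 9.2.3 gives the term, and 9.5 fits it. No rule in the plan is shown to give a wrong result, and no analysis depends on the point. At the risks quoted in 11.4.3 the readings differ by between 0 and 4.2 percentage points in the chance of reaching two subjects, and what would be reached is a discussion, not a stop.

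That range assumes independent participants with the same risk, and that infection and haemorrhage are the relevant harms. It also depends on the IMDD, which is not among the documents, so it cannot be checked whether any serious device effect falls between the two readings. Which events should count is for the sponsor and the DSMB, and this review takes no position on it. No change to the plan follows.

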9.3 Annual safety report

Not applicable (no investigational medicinal product).

9.4 Follow-up of adverse events

All adverse events will be followed until they have abated, or until a stable situation has been reached. Depending on the event, follow up may require additional tests or medical procedures as indicated, and/or referral to the general physician or a medical specialist.

9.5 Data Safety Monitoring Board (DSMB)

A Data Safety Monitoring Board will be established for this study. It will perform online safety surveillance and performs interim analyses on the safety data. It will consist of a committee

whose members are independent from the research group. The DSMB will consist of experts in the areas of this research, including neurology, implantable devices and ethics.

The task of the DSMB will be to monitor the progress in the study in terms of achieving the stated objectives and improvement of the listed parameters for BCI signal processing. The DSMB meets before the study starts or early in the course of the study, to discuss the protocol, the study, any analysis plan, future meetings, and to have the opportunity to clarify any aspects with the principal investigators. After that, the DSMB will meet at least once a year. Additional meetings may be planned depending on timing of inclusion of patients and progress. One of the (regular or additional) meetings will be scheduled shortly after the first patient has been followed for six months after implantation. The DSMB will be asked to give advice at the decision moment after the third implantation, as to how to proceed based on the obtained results. It is the responsibility of the DSMB to verify adherence of the research team with the procedures as described in the research protocol.

The recommendations of the DSMB are circulated and approved by all DSMB members, then forwarded to the PI and, if deemed necessary, to the Ethics Committee of the UMC.

Criteria for decision to terminate the study prematurely

The key criterion for premature termination of the study (also stated in Sections 4.4, 8.7 and 10.4) is level of proficiency at 6 months after implant ('futility'). In addition the usual criteria are relevant, being unexpected problems with function of the device, unexpected systematic side effects that cause concern ('safety'). In addition the DSMB may decide to advise termination of the pilot study if results are above expectations (i.e. high levels of proficiency in all three first participants, 'positive efficacy'), to expedite a larger clinical trial.

10. STATISTICAL ANALYSIS

Given the fact that this is a pilot study preparing for a larger clinical trial, the statistical analyses for the endpoints are descriptive, and will be considered separately for each individual subject.

10.1 Primary study parameter(s)

Primary endpoint is proficiency of use of the BCI system. The research aims to evaluate performance of the BCI system at the start of implantation, and to then optimize performance. Two levels of proficiency are formally tested on a regular basis.

First, the level of proficiency described as the primary objective, being *unsupervised BCI performance* (with the caregiver switching the UNP system from 'on' to standby' mode and vice versa), with the criterion that the system correctly detects a switch brain signal within 10 sec in a real life, cognitively engaging context, such as operating a spelling device. The formal test is based on this criterion, and constitutes copying a 30 character sentence within 30 minutes, with a margin of maximally 20% faulty characters (Level 2 proficiency). Once a patient has entered phase 3 (after completion of phase 2, which we expect to occur between 4 and 28 weeks after implantation, Section 15.4 for a schedule), the patient is asked to copy this predefined sentence during every scheduled visit of the research team. Depending on the performance and condition of the patient the task may be terminated before the end of the sentence. Speed, number of letters spelled and number of errors is recorded. The task is recorded on video. Once the patient has reached Level 2 proficiency, he has demonstrated that he can accurately control the BCI system using his brain signals, and the UNP performance with the respective patient will be designated as successful. Success of the complete study is defined as: At least 50% of participants (3/5) reach level 2 proficiency and can thus communicate effectively as assessed with a formal test.

Second, we define a lower level of proficiency, which represents a level equivalent to that of the communication channel that the patient had before participation, being *supervised BCI performance*. In the case of unreliable communication at the time of inclusion, the lower level of proficiency constitutes reliable yes/no communication. Once a week (starting from week 2, 3 or 4, depending on the postsurgical condition of the patient), a formal testing takes place (Level 1 proficiency), in which the patient has to perform the 'Communication Channel Verification Questionnaire' where he has to answer 20 questions with obvious yes/no answers (Section F1.3). These questions have to be answered using the BCI. In addition, the answers need to be detected each within a maximum period of 30 seconds. Each answer is obtained as follows: following presentation of the question, there are two consecutive 30-sec periods in which a brain signal can be generated by the patient, one period representing 'yes', the other 'no' (random order, indicated on a computer screen). If the patient wants to answer 'yes', he activates his BCI switch during the 'yes' phase and keeps it deactivated during the 'no' phase. Thus, each question lasts two times 30 seconds, and the total task lasts maximally 25 minutes (including time to actually state the questions). When 80% of the

questions were answered correctly (with 50% being chance level) on two occasions, the patient is considered to have achieved significant supervised BCI switch control. Training continues until the 'Communication Channel Verification Questionnaire' task criteria (a 80% score on two occasions/visits) are met with at least one of the control signals. When the patient has not reached this level of proficiency within 28 weeks after implantation, the training will be discontinued and the patient will be excluded from further study ([see Section 8.4](#)).

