8. METHODS

8.1 Study parameters/endpoints

8.1.1 Main study parameter/endpoint

Primary endpoint is proficiency of use of the BCI system. For this we recognize three levels of proficiency: First, the level of proficiency described as the primary objective, being *unsupervised BCI performance* (with the caregiver enabling / disabling AT device), with the criterion that the system correctly detects a switch brain signal within 10 sec in a real life, cognitively engaging context, such as operating a spelling device. A formal test has been designed, in which the patient has to copy a 30 character sentence within 30 minutes, with a margin of 20% faulty characters ([see Section 8.3.9, Level 2 proficiency](#)). For this test, scanning software is employed. Second, we define a lower level of proficiency, which represents a level equivalent to that of the communication channel that the patient had before participation, being *supervised BCI performance*, where the patient is able to generate switch commands with at least 80 % correct, with the help of a BCI researcher and/or caregiver (using a formal test, [see Section 8, Level 1 proficiency](#)). A third level of control is defined as *independent BCI performance*, where the patient is capable of enabling/disabling AT device control by himself. This requires the highest level of control achievable.

Thus, the three levels, in order of proficiency are:

- 1) Supervised use, dependent on continuous assistance for communication
- 2) Unsupervised use, ability to communicate without assistance for limited periods
- 3) Independent use, ability to communicate without assistance at any time of day or night.

Note that level 2 is the primary objective of the study, and that only levels 1 and 2 will be tested using formal tests. Success of the study is defined as: At least 50% of participants (3/5) reach level 2 proficiency and can thus communicate effectively as assessed with a formal test.

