Once a week (starting from week 2, 3 or 4, depending on the postsurgical condition of the patient), a formal testing takes place (Level 1 proficiency), in which the patient has to perform the 'Communication Channel Verification Questionnaire' where he has to answer 20 questions with obvious yes/no answers ([Section F1.3](#)). These questions have to be answered using the BCI. In addition, the answers need to be detected each within a maximum period of 30 seconds. Each answer is obtained as follows: following presentation of the question, there are two consecutive 30-sec periods in which a brain signal can be generated by the patient, one period representing 'yes', the other 'no' (random order, indicated on a computer screen). If the patient wants to answer 'yes', he activates his BCI switch during the 'yes' phase and keeps it deactivated during the 'no' phase. Thus, each question lasts two times 30 seconds, and the total task lasts maximally 25 minutes (including time to actually state the questions). When 80% of the questions were answered correctly (with 50% being chance level) on two occasions, the patient is considered to have achieved significant supervised BCI switch control. The 80% correct criterion is based on two sources of information:

- A published user questionnaire (Huggins et al., 2011), where 50% of ALS patients with mixed degree of paralysis stated that they would be satisfied with a BCI device that performs at least at 80% hit rate.
- The unwritten standard in EEG BCI that BCI control is achieved at and above 70% correct responses in a BCI task (Viduarre et al., 2010), which we want to exceed.

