11.2.2 Informed Consent

Executive Summary

This document describes in detail the informed consent procedure, including explanation of the project, testing of the reliability of the communication channel and the patient's understanding of the project.

Full description of procedures

Since patients will have a strong difficulty to communicate and will not be able to sign an informed consent form, the informed consent procedure will be recorded using a regular digital video camera. The acquired video file will be converted into at least 3 different formats (.avi, .mpeg and .mov), and those will be saved on DVD, as well as on our in house data server, which is backed up every day.

Besides the patient, three people will be present during the procedure: 1 confidant of the patient, 1 member of the research team and an independent observer. The informed consent procedure will involve the following steps:

- First, the best possible communication channel with the patient will be determined. Patients should at least be able to give clear responses by e.g. severely compromised speech, a switch, eye blinks etc.
- In order to test the reliability of the communication channel (most likely only a switch-like signal, such as an eye movement), 10 pairs of simple and irrelevant questions will be asked ([see Section F1.3](#)). Each of these questions will be followed by a yes and no option, to which patients may respond, making the number of possible choices 40. Patients need to select > 95% (=38/40) of these choices correctly, to be able to proceed with the rest of the informed consent procedure. In case of very subtle movements, we will repeat each question 2 times and take the majority (2/3 or 3/3) of the yes/no responses per question as the answer. Of these answers, 95% needs to be correct to proceed with the informed consent procedure.
- The complete project will be once more explained verbally to the patient and his/her relatives. This information will include the following:
 - the purpose of the research
 - the expected duration of the subject's participation
 - a description of the procedures to be followed and an identification of all the procedures which are considered experimental
 - risks and benefits
 - the extent to which confidentiality of records identifying the subject will be maintained
- The patient and his/her relative will be asked if they have any further questions. If yes, these questions will be answered.

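### Passing Level 1 (16 of 20 questions) does not show equivalence to the prior communication channel, which had to score 38 of 40 choices at the standard entry test

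*Combined protocol and SAP*

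**What the plan says.** Level 1 (supervised use) is one of the two formally tested levels of the primary endpoint. Section 8.1.1 says that it "represents a level equivalent to that of the communication channel that the patient had before participation". Section 10.1 repeats this, again calling it "a level equivalent to that of the communication channel that the patient had before participation", and so does the endpoint paragraph of the Summary.

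The Level 1 test is the Communication Channel Verification Questionnaire (Section F1.3), "where he has to answer 20 questions with obvious yes/no answers" by means of the BCI. Each question has a 30-second yes window and a 30-second no window. The criterion in Section 8.3.9 is "When 80% of the questions were answered correctly (with 50% being chance level) on two occasions". Section 10.1 repeats it as "a 80% score on two occasions/visits) are met with at least one of the control signals". Section 8.3.9 gives two reasons for 80%: a survey of what potential users would accept, and the wish to exceed a 70% convention in EEG-based BCI.

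The prior channel is tested in Section 11.2.2, also with F1.3: "10 pairs of simple and irrelevant questions will be asked", each with a yes and a no option, "making the number of possible choices 40". The pass mark is: "Patients need to select > 95% (=38/40) of these choices correctly". For very subtle movements each question is put three times, the majority response counts, and 95% of those answers must be right. Under Section 11.2.1, repeated scores below these criteria mean non-inclusion unless there is evidence that the patient earlier expressed the will to participate.

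For participants with unreliable communication at inclusion, Section 10.1 replaces the comparison with the prior channel by reliable yes/no communication.

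**The concern.** The protocol describes Level 1 as matching the old channel, but its pass mark is lower than the one the old channel had to meet on what appears to be the same instrument. Neither reason given for 80% refers to the prior channel. Section 10 plans no comparison with it and states no equivalence margin; the analysis is descriptive, subject by subject.

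What is at stake is how a Level 1 result is read. Level 1 opens phase 3, decides withdrawal at 28 weeks, and enters the evaluation after three participants. An investigator, a DSMB member or a reader of the final report who meets a participant with Level 1 only, and takes the definition at its word, would conclude that the implant has reproduced the earlier level of communication. The test does not show that.

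**Working it through.** **Inputs.** Level 1: 20 questions, 80% (Sections 8.3.9 and 10.1). Entry test: 10 pairs, so 20 questions; two options each, so 40 choices; pass mark 38/40 (Section 11.2.2). Majority route: three presentations per question, 95% of majority answers (Section 11.2.2).

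**Step 1: the plan's own figures.** 38/40 = 0.950, so the stated figure reproduces as at least 95%. Strictly more than 95% would need 39/40 = 0.975. The more lenient 38/40 is used here. Level 1: 0.80 × 20 = 16 questions.

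**Step 2: put both on one scale.** A wrongly answered question contains at least one and at most two wrong choices.

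| | Questions right (of 20) | Choices right (of 40) |
|---|---|---|
| Entry pass mark | 20 − 2 = 18 to 20 − 1 = 19 (90–95%) | 38 (95%) |
| Level 1 pass mark | 16 (80%) | 40 − 8 = 32 to 40 − 4 = 36 (80–90%) |

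The gap is 10 to 15 percentage points per question, or 5 to 15 per choice. At the pass marks, Level 1 tolerates four wrong questions and the entry test one or two. A session at 16/20 fails 38/40 however its errors fall. So does one at 17/20, which gives at most 37/40.

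**Step 3: does the scoring rule matter?** The plan does not say how a question is scored if the switch is activated in both windows or in neither. The table covers the rule that both windows must be right. If instead each question yields one forced answer, which fits the stated 50% chance level, a wrong answer means two wrong choices. Then 16/20 is 32/40, and 38/40 is 19/20. The direction is the same.

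**Step 4: the majority route.** With one majority answer per question, 95% is 19/20. If the three responses are independent with single-response accuracy p, majority accuracy is 3p² − 2p³. Setting this to 0.95 gives p ≈ 0.865, about 6.5 points above 0.80. At p = 0.80, majority accuracy is 1.920 − 1.024 = 0.896, and 19/20 or better is reached with probability 0.37. The gap is narrower on this route but does not close.

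**Step 5: illustration per question.** Assume independent questions and a true accuracy of 80%. One session then reaches 16/20 with probability 0.63, 18/20 with 0.21 and 19/20 with 0.07. Requiring 80% on two occasions repeats the same mark; it does not raise it to 18 or 19.

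**The case against.** The best defence is that the word equivalent is meant functionally. The three levels are ordered by how much help the participant needs, and Level 1 resembles the assisted, switch-like communication that these patients already have. The plan contains no equivalence hypothesis, and the conclusion it draws from a pass is only significant supervised switch control. The two thresholds also serve different ends: 95% safeguards consent, and Level 1 has a 30-second limit that Section 11.2.2 does not state for the entry test. This does not rescue the wording. The text speaks of a level of proficiency and measures it by percentage correct; if only the kind of channel is meant, the protocol should say so.

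Other parts of the defence stand, and they rule out stronger readings that a reader might infer:

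- **That a participant who passes Level 1 communicates less accurately than before.** Both figures are floors, and someone who passes may score 20/20. Nor could 20 questions settle it: 16/20 against 18/20 gives a Fisher exact p of 0.66, and 16/20 against 19/20 gives 0.34.
- **That the contradiction covers every participant.** Those with unreliable communication may enter without meeting 95%, and Section 10.1 gives them another anchor.
- **That a decision is affected.** Success for a participant and for the study requires Level 2. Phase 3 entry, the 28-week withdrawal and the three-participant evaluation use the 80% criterion; none uses the equivalence phrase.
- **That a per-window accuracy, taken as the square root of 80%, gives the chance that a Level 1 channel would pass the entry check.** That model needs two independent windows to be right, which implies 0.5 × 0.5 = 25% by chance. The protocol states 50%.

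**Conclusion.** The point holds in a limited form. For participants included through the standard communication test, a Level 1 pass does not show equivalence to the prior channel: 16/20 questions is at most 36/40 choices, against a required 38/40, and 16 questions compares with 18 to 19 on the question scale. This part is counting and needs no probability model. The figures for the majority route and the session probabilities assume independence and are illustrations only.

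One assumption remains. F1.3 itself is not among the documents supplied, so that both tests use the same instrument rests on the shared section number and the matching format of 20 yes/no questions.

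The documents do not support saying that 80% is the wrong threshold, that those who pass are worse off than before, or that study success is compromised. The defect is a property claimed for part of the primary endpoint that its test does not deliver. It should be corrected because it governs what a Level 1-only result may be said to show.

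**What to change.** In the Summary, Section 8.1.1 and Section 10.1, delete the statement of equivalence to the prior channel. Describe Level 1 in the protocol's own terms: significant supervised BCI switch control, meaning at least 80% of 20 yes/no questions correct on two occasions. Do not replace the claim with a label saying that Level 1 lies below the consent standard; that would misdescribe anyone who scores above the floor, and anyone whose legal representative signed consent.

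In Section 10.1, for participants who took the entry test, add a descriptive line giving the Level 1 score next to the participant's own entry F1.3 score. Score both per question, and note where majority voting was used, since those scores are not directly comparable with single responses. Base any statement about equivalence on that descriptive comparison only.

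The 80% threshold and the decisions tied to it do not change. The cost is three wording edits, one descriptive line from tests the plan already administers, and a slightly less favourable description of Level 1.
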